6. PARTICIPANT IDENTIFICATION AND RECRUITMENT

6.1. Study Participants

Adult patients (≥ 18 years old) in participating wards who have been on mechanical ventilation for more than 48 hours.

6.2. Inclusion Criteria

- a. Patients 18 years and older
- b. Invasive mechanical ventilation ≥ 48 hours
- c. Satisfy the US Centers for Disease Control and Prevention National Healthcare Safety Network VAP diagnostic criteria [29]
 - o At least one of the following:
 1. temperature $> 38^{\circ}\text{C}$
 2. white blood cell count $\geq 12,000 \text{ cells/mm}^3$ or $\leq 4,000 \text{ cells/mm}^3$
 3. altered mental status with no other causes in > 70 year-olds; AND
 - o Two or more chest imaging tests demonstrating at least one of the following:
 1. new and progressive OR progressive and persistent infiltrate
 2. new and persistent OR progressive and persistent consolidation
 3. new and persistent OR progressive and persistent cavitation, AND
 - o At least two of the following:
 1. new onset of purulent sputum, or change in character of sputum, or increased respiratory secretions, or increased in suctioning requirements
 2. new onset or worsening tachypnea or dyspnea
 3. rales or bronchial breath sounds
 4. worsening gas exchange defined by oxygen desaturations (e.g., $\text{PaO}_2/\text{FiO}_2 < 240$), increased oxygen requirements or increased ventilation demand
 - 5.

6.3. Exclusion Criteria

- a. Poor likelihood of survival as defined by a Sepsis-related Organ Failure Assessment score (SOFA score) of >11 points [38]
- b. Immunocompromised patients (HIV with CD4 <200 cells/mm³, corticosteroids > 0.5 mg/kg per day for > 30 days, received chemotherapy in the past 3 months, solid organ or hematopoietic cell transplant)
- c. Patients receiving antibiotic therapy for any other defined extra-pulmonary infections that warrant a duration of antibiotics longer than 7 days or complications of pneumonia such as lung abscess or empyema that warrant a duration of antibiotics longer than 7 days (excluding anti-tuberculosis treatment, antifungal medications, antibiotics meant for chronic suppression of chronic infections or chronic obstructive lung disease)
- d. Patients who have been treated for VAP for more than 7 days from screening
- e. Vulnerable population including prisoners and refugees

7. STUDY PROCEDURES

7.1. Recruitment

Relevant sub-specialists such as general medicine, respiratory, infectious disease, intensive care and anaesthesia physicians, nurses and pharmacists involved in the care of ventilated patients from all participating sites will be briefed on the study protocol in advance. With their support, a site PI will be nominated to head the study.

The study team will do screening for potential subjects. Potential subjects are identified according to the eligibility criteria stated above. When a potential subject is identified, our study team will approach the primary physician for his/ her permission for the study team to speak to the patient or patient's legal representative or patient's next-of-kin (NOK) for consent. Patient's legal representative or NOK may be then contacted via phone call or in person. Discussion and explanation of the study procedures and signing of the consent will be done face-to-face.

7.2. Screening and Eligibility Assessment

Screening will be done on all mechanically ventilated patients in the respective study sites according to the eligibility criteria stated above. Participants should be recruited into the study as soon as possible after screening. A maximum of 72 hours is allowed between screening (fulfilment of the inclusion/exclusion criteria) and recruitment.

7.3. Informed Consent

Participants' legal representatives or NOKs will be asked to represent the participants if the participants are sedated and do not have the capacity to make informed decision to participate in the study. The participants, their legal representatives or NOKs must personally sign and date the latest approved version of the Informed Consent form before any study specific procedures are performed.

Written and verbal versions of the Participant Information and Informed Consent will be presented to the participants, their legal representatives or NOKs detailing no less than: the exact nature of the study; what it will involve for the participant; the implications and constraints of the protocol; the known side effects and any risks involved in taking part. It will be clearly stated that the participant, his/her legal

representative or NOK (on behalf of the participant) is free to withdraw from the study at any time for any reason without prejudice to future care, and with no obligation to give the reason for withdrawal.

The participants, his/her legal representatives or NOKs will be allowed sufficient time to consider the information, and the opportunity to question the Investigator or other independent parties to decide whether they will participate in the study. Written Informed Consent will then be obtained by means of participants', their legal representatives' or NOKs' dated signatures and dated signature of the person who presented and obtained the Informed Consent. The person who obtained the consent must be suitably qualified and experienced, and have been authorised to do so by the Investigator. A copy of the signed Informed Consent will be given to the participants, their legal representatives or NOKs. The original signed form will be retained at the study site.

When the participants are deemed to have decision-making capacity by the primary physicians, he/she will be re-consented with the same procedures as above.

The concurrent prospective data on clinical cultures, antibiotics utilisation, adaption and compliance of VAP prevention bundles and hand hygiene rates will involve all participating wards throughout the period of the study. All patients admitted to these units will be included as part of this audit and consents will not be taken for this purpose. All information collected as part of the audit will be anonymised to ensure patient confidentiality.

As the time window for consent taking is limited, and visitation restrictions during the COVID-19 pandemic, oral consent may be used for participant enrolled temporarily. When oral consents are taken, the study team will be recording the information in the "research record for oral consent" (version 1.0, 8th July 2021). Written consent will be obtained as soon as direct contact with participant or participant's family is possible according to the local hospital policies.

7.4. Randomisation, blinding and unblinding

Randomisation will be done via stratified block randomisation by the study sites to ensure participants with similar characteristics such as gender and age are distributed equally in the intervention and control groups. Randomisation will be done with a computer programme with a seed to allow reproducibility. Randomisation will be done with a 1:1 ratio. To prevent predictability of the random sequence, generation of the randomisation sequence is performed by an independent statistician and details of the randomisation generation is unavailable to all investigators. Randomisation will be allocated using sequentially numbered opaque envelopes. Fitness criteria for randomisation (section 8) must be met prior to randomisation.

Patients will be blinded to the study, as they will not be informed of the treatment duration and likely to be sedated and unaware of the treatment regimens. Investigators will be blinded during the assessment of the participants for clinical stability based on the above-described criteria to minimise observer bias. Once conditions for stopping antibiotics are satisfied, the investigator will be unblinded and contact the primary physicians to stop antibiotics. The physicians will remain blinded until they are informed that the participant is suitable to stop antibiotics. Independent assessors, who are assigned to determine pneumonia recurrences, will be blinded from the randomisation arms. This will be achieved by blinding all study details, including randomisation arms, for participants with potential recurrences from these independent assessors.

7.5. Baseline Assessments

At recruitment, participants' demographics, medical history, antibiotics administration record, chest X-ray or other imaging findings, biochemical, microbiological and haematological results and clinical parameters will be collected. These are routine investigations ordered by the clinical teams taking care of the patients. Stool samples and upper and lower respiratory tract samples will be collected if they have not already been collected in the 24 hours prior to recruitment.

7.6. Subsequent Visits

Clinical information will be collected during participant's hospitalisation. Two follow-ups will be done on day 28(± 5) and 60(± 5) after recruitment. During these visits, similar clinical information will be collected (if available) via hospital record review. Repeat respiratory and stool sample will also be collected. In the event that the participants are not able to attend the follow-ups in person, a telephone interview can be done in place of a physical visit.

7.7. Sample Handling

Respiratory cultures will be collected with the usual volume of 5-10ml per sample. Respiratory cultures may be collected via ETT, BAL or any other methods that the primary physician and local microbiology laboratories routinely use. Stool culture will be collected following defecation with the usual volume of 10-50g per sample. Stool samples are collected at recruitment, weekly during hospitalisation and day 28/60(± 5) after enrolment.

Microbiology cultures will be processed and reported in the local laboratories, which are expected to have standing quality control measures. Isolates, once identified, will be preserved, frozen and transported to an Oxford or Singapore study laboratory for genomic studies. These genomic results should concur with the initial microbiology laboratories' identification of the isolates.

a) Respiratory cultures

All samples will be cultured and identified via standard microbiological methods. Susceptibility studies will be performed using EUCAST or CLSI agar method and breakpoints. Culture results with antibiogram are usually available within 48 to 72 hours after sample collection.

Pathogens causing VAP and colonising MDROs will be processed for DNA extraction and undergo whole genome sequencing. These sequencing data will be used to track the spread of pathogens between hosts allowing for unobserved infection times, multiple independent introductions of the pathogen, and within-host genetic diversity.

These isolates will be de-identified and stored for up to 15 years for use in future ethically approved studies. We will seek permission from the participants to store their samples and include this in the informed consents.

b) Respiratory and stool samples

For microbiome analysis, respiratory and stool samples will be processed for DNA extraction. Shotgun metagenomics approach will be used to characterise microbial community dynamics in the respiratory and intestinal tract. The characteristics of the microbiota will be determined by comparing alpha and

beta diversity metrics between the groups of patients to explore the short- and long- term impact of the various durations of antibiotics in individual patients. The data will also be used to assess if alterations in the repertoire of antibiotic resistant genes can be detected, and to study shifts in functional and metabolic capacity during the time course with a view to getting mechanistic insights into potentially protective components of the microbiome.

These isolates will be de-identified and stored for up to 15 years for use in future ethically approved studies. We will seek permission from the participants to store their samples and include this in the informed consents.

c) Bacterial isolates from other routine clinical cultures such as blood, cerebral spinal fluid, pus etc

All bacterial isolates including MDR *Acinetobacter spp*, *Pseudomonas spp*, *Enterobacteriaceae*, *Staphylococcus aureus* and *Enterococcus spp*, grown from other routine clinical cultures will be de-identified and stored for up to 15 years for use in future ethically approved studies. In the current study, these isolates will undergo whole genome sequencing to compare the within-host evolution of resistant organisms. We will seek permission from the participants to store their samples for up to 15 years in the informed consents.

7.8. Discontinuation/Withdrawal of Participants from Study

Each participant or NOK has the right to withdraw from the study at any time. The reason for withdrawal will be recorded in the Case Report Form. Withdrawal from the study will not result in exclusion of the data for that participant from analysis.

In addition, the Investigator may discontinue a participant from the study at any time if the Investigator considers it necessary for any reason including but not limited to:

- Ineligibility (either arising during the study or retrospectively having been overlooked at screening)
- Significant protocol deviation
- Significant non-compliance with treatment regimen or study requirements
- Loss to follow up
- Failure to meet fitness criteria by day 7

We will compare baseline characteristics between patients who had protocol violations or who were unavailable for follow-up with those who did not. Follow-ups and data collection listed on the standard CRF for discontinued participants, including those who fail to be randomised, will be carried out within day 60(± 5) of enrolment.

Discontinued subject can be rescreened (under a new number). If the subject is rescreened, a new subject number will be allocated. The above patients will not be followed up once withdrawn or discontinued, and replaced to achieve the calculated sample size.

7.9. Definition of End of Study

The end of study is the date of the last follow-up visit of the last participant.

Persistent VAP or treatment failure is defined as the lack of improvement of hemodynamic stability or ventilation requirements without an alternative cause other than the same episode of VAP. These patients will be continued to be monitored for the above-described “fitness criteria” and antibiotics should be stopped when they eventually meet the criteria. Recurrent VAP is defined as an additional episode of VAP satisfying the CDC clinical and radiological criteria of VAP [29] following commencement of the primary VAP treatment within 60(+5) days of enrolment. Opinion from 2 respiratory experts blinded to the randomisation will be sought to diagnose persistence and recurrences. Patients who are diagnosed with an alternative source of infection or a complication from VAP such as lung abscess or empyema that warrant a duration of antibiotics longer than 7 days prior to the last day of assigned duration of antibiotics are not considered treatment failures. These patients will not meet fitness criteria for randomisation and be discontinued from the study and subsequent analysis (see section 7.8). In cases where patients randomised to short duration and satisfy the above-described “stop criteria” but did not have their antibiotics stopped by day 7, they are considered protocol deviations. They will be analysed with intention to treat analysis.

Duration of antibiotics in control group will be at least 8 days with the exact duration decided by the managing physicians.

Adverse events will be recorded throughout the study period, including *C. difficile* infection, acute kidney injury, hepatitis, drug allergies, haematological and other complications.

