Participants in the intervention (short duration) arm will receive antibiotics for up to 7 days. Antibiotics should be stopped from day 3 to 7 if respiratory cultures are negative and the patients fulfil a set of stringent clinical criteria signifying cardiopulmonary stability for 48 hours. If the respiratory cultures are positive, patients who fulfil the same set of clinical criteria should have their antibiotics stopped from day 5 to 7 (see section 8. Interventions). Antibiotics administered via all routes i.e. intravenous, oral and nebulisation should be stopped. Randomisation will be carried out when the participants fulfil the clinical stop criteria. The rationale for stopping antibiotics at the above time points is as follows:

Group 1: Short Duration arm

(a) Day 3

Patients who have negative respiratory cultures should have their antibiotics stopped from day 3 to 7 if the patient satisfies a set of criteria signifying clinical stability. As discussed above, though there are no randomised studies to support this, there are 2 observational studies [32, 33] showing that discontinuation of antibiotics in these cases did not result in a higher mortality or rate of new respiratory infections compared to those whose antibiotics were continued. In addition, those whose antibiotics were withheld had a lower rate of total secondary infections by MDROs. One of these studies concluded that antibiotics could be safely discontinued in patients with negative respiratory cultures with no significant impact on mortality, despite persistence of signs and symptoms of pneumonia in 35% of these patients [32]. The above studies have led to the recommendation in the 2016 IDSA/ATS guideline that for patients with suspected VAP whose respiratory invasive culture results are below the diagnostic threshold for VAP, antibiotics should be withheld rather than continued [3].

(b) Day 5-7

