2. BACKGROUND INFORMATION

2.1. Objectives

Primary objective

To assess the effect of short (7 days or fewer depending on clinical response) versus long (8 days or more depending on physicians' preference) antibiotic treatment strategies on mortality and pneumonia recurrence within 60 days of enrolment in adults with ventilator-associated pneumonia (VAP) in Asia.

Secondary objectives

To compare the following endpoints according to treatment allocation within 60 days of enrolment:

- a) Ventilator-associated events
- b) Duration of mechanical ventilation
- c) Duration of hospitalisation
- d) Acquisition of multidrug resistant infection or colonisation during the hospitalisation
- e) Number of days of exposure to antibiotics during hospitalisation
- f) Number and types of extrapulmonary infections during hospitalisation (determined from cultures taken from sterile sites)
- g) Adverse events, i.e. antibiotic related diarrhoea, allergic reactions, readmissions

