2.2. Study Design

The study design is a randomised, partially double-blinded (blinding may be achieved up to 7 days) controlled trial to assess the efficacy of short versus longer antibiotics course in adults with VAP. The trial has a stepwise noninferiority–superiority hypothesis, i.e. if non-inferiority of short duration, compared with long duration, is shown, statistical tests for superiority will be performed using closed testing methods without requiring adjustment of the significance level for multiple comparisons.

Period of external pilot	19 February 2018 to 23 May 2018
Date of start of recruitment	25 May 2018
Date of end of recruitment	16 December 2022
Date of end of follow-up	14 February 2023
Date of expected analysis	14 March 2023 to 14 May 2023
target number of participants	460 (230 per arm)

Participating study sites include:

- 1) National University Hospital, Singapore
- 2) Tan Tock Seng Hospital, Singapore
- 3) Sunpasitthiprasong Hospital, Ubon Ratchathani, Thailand
- 4) Srinagarind Hospital, Khon Kaen, Thailand
- 5) Patan Academy of Health Science, Patan Hospital, Kathmandu, Nepal
- 6) Civil Hospital, Kathmandu, Nepal
- 7) Khon Kaen Hospital, Khon Kaen, Thailand
- 8) Cajuru University Hospital, Pontifical Catholic University of Paraná, Brazil

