In the short duration arm, all antibiotics should be withdrawn by day 7 (short duration) according to the randomisation assignment, except for those participants with treatment failure in the case of persistent VAP or a new-onset infection of a different source prior to the last day of assigned duration of antibiotics. Persistent VAP or treatment failure is defined as the lack of improvement of hemodynamic stability or ventilation requirements without an alternative cause other than the same episode of VAP. These patients will continue to be monitored for the above-described “fitness criteria” and antibiotics should be stopped when they eventually meet the criteria. Recurrent VAP is defined as an additional episode of VAP satisfying the CDC clinical and radiological criteria of VAP¹ following commencement of the primary VAP treatment within $60(\pm 5)$ days of enrolment. Opinion from 2 respiratory experts blinded to the randomisation will be sought to diagnose persistence and recurrences. Patients who are diagnosed with an alternative source of

infection or a complication from VAP such as lung abscess or empyema that warrant a duration of antibiotics longer than 7 days prior to the last day of assigned duration of antibiotics are not considered treatment failures. These patients will not meet fitness criteria for randomisation and be discontinued from the study and subsequent analysis. In cases where patients are randomised to short duration and satisfy the above-described “stop criteria” but did not have their antibiotics stopped by day 7, they are considered protocol deviations. They will be analysed in the intention to treat analysis according to arm they are randomised to.

Duration of antibiotics in the control group will be at least 8 days with the exact duration decided by the managing physicians.

Adverse events will be recorded throughout the study period, including *C. difficile* infection, acute kidney injury, hepatitis, drug allergies, haematological and other complications, readmissions.

Blinding

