2.6. Hypotheses and Definition of Primary and Secondary Outcomes

Primary end point

The primary end point of the study is the difference in the proportion of participants with the composite endpoint of death and VAP recurrence rate within 60(± 5) days of enrolment.

Death refers to all-cause mortality. VAP recurrences are episodes which satisfy the US CDC VAP criteria, and verified by two independent respiratory or infectious diseases physicians blinded to the randomisation arm.

The first statistical test for the primary end point will be for non-inferiority. Here, the null hypothesis (H_0): $\theta \geq \delta$ will be tested against the alternative (H_1): $\theta < \delta$, where θ is the treatment effect difference between the proportion of participants who have the primary outcome in the short and long treatment strategy groups, and δ is the fixed non-inferiority margin of 12%.

In the event that short is non-inferior to the long treatment strategy, standard two-sided superiority testing will be performed. That is, the null hypothesis (H_0): $\theta = 0$ will be tested against the alternative (H_1): $\theta > 0$, where θ is the treatment effect difference between the proportion of participants who have the primary outcome in the short and long treatment strategy groups.

Secondary end points

All statistical tests for the secondary endpoints are standard two-sided superiority tests.

a) Ventilator-associated events

Definition: Events which satisfy the US CDC VAP criteria ¹ but were not verified by two independent respiratory or infectious diseases physicians.

H_0 : There is no difference in the proportion of participants who have ventilator-associated events in the short and long treatment strategy groups, i.e. $\theta^{VAE} = 0$;

H_1 : There is a difference in the proportion of participants who have ventilator-associated events in the short and long treatment strategy groups, i.e. $\theta^{VAE} \neq 0$;

where θ^{VAE} is the treatment effect difference between the proportion of participants in the short and long treatment strategy groups.

b) Duration of mechanical ventilation

Definition: Total duration of mechanical ventilation during the 60 days of follow-up after enrolment.

H_0 : There is no difference in the total duration of mechanical ventilation in the short and long treatment strategy groups, i.e. $t^v_s = t^v_l$;

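### The primary endpoint has no single closing day (day 60 or up to day 65), and its recurrence component can count an episode that occurs before randomisation

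*Protocol*

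**What the plan says.** **Closing point.** The recurrence definition in Protocol 8 counts an additional episode "following commencement of the primary VAP treatment within 60(+5) days of enrolment". SAP 2.4 repeats that definition with ±5 in place of +5. The primary end point in SAP 2.6 is the "composite endpoint of death and VAP recurrence rate within 60(± 5) days of enrolment", and Protocol 4 has the same window. The primary objective in SAP 2.1 concerns "mortality and pneumonia recurrence within 60 days of enrolment", with no tolerance. SAP 2.7 assesses mortality weekly over days 0 to 60 and screens for recurrence from day 0 to discharge. Protocol 5 (Follow-up visits) has the composite assessed at a visit at 60(±5) days, and Protocol 7.6 allows a telephone interview instead.

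**Opening point.** The recurrence definition starts at commencement of treatment for the index pneumonia. Protocol 5 says: "Randomisation will be carried out when the participants fulfil the clinical stop criteria". SAP 2.7 makes day 0 the day of enrolment and places randomisation in days 0 to 7.

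**Handling.** SAP 7.1 analyses a binary outcome because recorded dates may reflect when an event was observed. It scores incomplete follow-up without an event as no event. SAP 7.4 calls for multiple imputation when complete outcome data fall short of a 95% threshold, counting losses before 60 days. SAP 2.2 gives 16 December 2022 as the end of recruitment and "14 February 2023" as the end of follow-up.

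**The concern.** A tolerance that belongs to a clinic visit has been written into the definition of the endpoint. With no governing wording and no truncation day, someone must decide at analysis whether events on days 61 to 65 count. SAP 9.2 says that the trial statistician is not blinded, so that choice could be made with the allocation known.

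The status of a last contact on days 55 to 59 is also open. It is complete under ±5 but lost before 60 days under SAP 7.4, so the ambiguity can affect whether the imputation analysis is triggered.

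The opening point is a separate matter. An episode after enrolment but before randomisation cannot be an effect of allocation. Such events are expected equally in both arms and shrink the risk difference, which in a non-inferiority comparison favours the conclusion being tested. Only recurrence is affected, because a randomised participant cannot have died before randomisation.

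**Working it through.** The plan gives no figure for either end of the window. From Protocol 10 (The Number of Participants) and SAP 2.5 I use an event proportion of 55% in both arms, a 12-point margin, one-sided 5% and 412 evaluable participants (206 per arm). As a check on that setting, the fixed-design normal approximation gives 78.9% power at 412, against the stated 80%.

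**1. The closing rules side by side**

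| Place | Closes at | Death on day 63 |
|---|---|---|
| Protocol 8 (recurrence only) | 60(+5) | not applicable; a day-63 recurrence is inside |
| Protocol 4, SAP 2.6 | 60(±5) | inside the tolerance |
| SAP 2.4 (recurrence only) | 60(±5) | not applicable; a day-63 recurrence is inside |
| SAP 2.1 | 60 | not an event |
| SAP 2.7 (mortality) | 0 to 60 | outside the schedule |

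At the upper end +5 and ±5 agree on day 65. The conflict that matters is day 60 against day 65.

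**2. Calendar.** From 16 December 2022, 15 days reach 31 December, 46 reach 31 January and 60 reach 14 February 2023. Day 65 would be 19 February. The stated end of follow-up fits a day-60 cut-off, but the last recruits could not be observed on days 61 to 65.

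**3. Size of the closing ambiguity.** The documents give no event times, so two late hazards are assumed, and an assumed 2-day difference between arms in mean cut-off.
- Constant hazard: λ = −ln(0.45)/60 = 0.0133 per day. Risk at day 60 is 55.0%, and at day 62 it is 1 − exp(−62λ) = 56.2%. The difference is about 1.2 points.
- Late hazard of 0.3% per day among the 45% event-free: 0.45 × 0.003 × 2 = 0.0027, about 0.3 points.

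If visit timing is the same in both arms, there is no shift of this kind.

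**4. Size of the opening problem.** Let q be the share in each arm with a counted recurrence before randomisation (assumed). A true 12-point excess in the rest appears as d = 0.12 × (1 − q). With 55% in the long arm, 55% + d in the short arm and 206 per arm:

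type I error = Φ((0.12 − d)/SE − 1.645)

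For q = 5%: d = 0.114, SE = √(0.55 × 0.45/206 + 0.664 × 0.336/206) = 0.0478, and Φ(0.006/0.0478 − 1.645) = Φ(−1.52) = 6.4%.

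| q | Apparent excess (points) | One-sided type I error |
|---|---|---|
| 0 | 12.0 | 5.0% |
| 1% | 11.9 | 5.3% |
| 3% | 11.6 | 5.8% |
| 5% | 11.4 | 6.4% |

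This is a fixed-design approximation that ignores the interim looks.

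**The case against.** The strongest reply is that this is loose wording around an endpoint that is really day 60. Mortality is assessed weekly to day 60. SAP 5.3, SAP 7.4 and most secondary definitions in SAP 2.6 use 60 days, and follow-up ends exactly at day 60 for the last recruits. SAP 5.7 has everyone followed weekly at the same frequency, and recurrences are adjudicated blind. This makes day 60 the most plausible intention. It does not settle the matter, because the formal end point statement in SAP 2.6 says 60(±5).

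The +5 in Protocol 8 may be a slip or a loss in text extraction. Nothing here depends on it.

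On the opening, the reply is that counted recurrences before randomisation should be rare. The gap is about a week at most. Temperature and haemodynamic criteria must be met first, and two blinded experts must judge the episode a recurrence rather than persistent pneumonia, which is defined separately. I accept this, and it is why the assumed range starts at 1%.

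Four stronger readings are tempting, and the documents do not support them:
- **Each participant's cut-off is the visit date.** This can be inferred from Protocol 5 and SAP 7.1, but neither document says it.
- **The SAP's dates contradict its window.** They are consistent with a day-60 cut-off, and day 60 lies inside 60(±5).
- **The tolerance is worth half the margin.** Under a constant hazard, cumulative risk runs from 51.9% at day 55 to 57.9% at day 65. That 6-point spread is within an arm and is not comparable with a between-arm margin unless one arm were cut at day 55 and the other at day 65.
- **Episodes before enrolment count.** The definition is also bounded by days of enrolment, so the exposed interval is from enrolment to randomisation.

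**Conclusion.** The point holds as an unresolved definition of the primary endpoint with a small expected effect. The passages give day 60 and day 65 as closing points without a governing rule, and the recurrence definition admits episodes before randomisation.

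The closing ambiguity is mainly noise, since the same window applies to both arms. It biases the comparison only if visit timing or late ascertainment differs by arm. Sites know the allocation by then, but nothing in the documents indicates such a difference. An assumed 2-day difference is worth about 0.3 to 1.2 points.

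The opening has a known direction, towards non-inferiority. Type I error rises to about 5.3% to 6.4% for an assumed 1% to 5% of participants, and the lower end is the more plausible. The hazards, the 2-day difference and q are all assumptions.

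The main reason to act is that a fixed rule removes a choice of cut-off that could otherwise be made after unblinded data are seen.

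**What to change.** Use one definition in Protocol 4, 5, 8 and 10 and in SAP 2.1, 2.4, 2.6 and 2.7: death, or verified recurrence with onset after randomisation, on or before day 60 from enrolment.

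- Keep ±5 only as the visit window for ascertaining day-60 status. A last contact before day 60 needs a record or telephone check of status at day 60.
- List events dated after day 60 without counting them.
- Date a recurrence by the day the CDC criteria were first met.
- Confirm that the CRF captures dates of death and recurrence, and add them to the 100% check in SAP 3. The dates listed there do not name either, and SAP 7.1 warns that dates may reflect observation.

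**Cost.** This is mostly wording, plus a status check for early contacts. It costs more if the CRF lacks the two dates. A few events on days 61 to 65 would no longer count. Time at risk after randomisation would still vary by up to about 7 days (roughly 53 to 60), because the clock runs from enrolment and randomisation falls on days 0 to 7.
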